- fertility (planned or unplanned), length of gestation, prior hysterotomy condition (uterine incision created at the time of open fetal surgery) at the time of future delivery, complications from potential uterine dehiscence/rupture.

- fertility concern for having undergone an invasive uterine procedure: evaluation of patient concerns for future pregnancy(ies) and depression.

Please save frequently

c) **Describe the study design (e.g., single/double blind, parallel, crossover, control, experimental, observational, etc.). If the study is investigator-initiated, a timeline for individual subject recruitment, follow-up, and analysis for the study is required. Also, indicate if the subjects will be randomized.**

This is an Investigator initiated, prospective study reviewing medical records and performing a sonohysterogram on non-pregnant women at 6 or more months after delivery of an infant who received open fetal repair.

d) **If subjects will be given placebo, please justify placebo use. *?HELP?***

Protocol Title: Evaluation of Hysterotomy Site after Open Fetal Surgery

n/a

3. Study Procedures

a) N Is this project a multicenter study (i.e., same project is conducted elsewhere by a different investigator) OR does this study involve conduct of research at multiple sites? Is SLU acting as a coordinating center for other sites OR is the SLU PI a direct recipient of a federal grant for this research? If yes, complete and attach the Supplemental Application for Coordinating Center Activities. Will the SLU site be participating in all parts/procedures/arms of the study?

If No, explain what SLU will NOT participate in:

Please save frequently

Page numbers from a sponsor's protocol/grant may be referenced in 3b, 3c, and 3d.

b) Describe all the procedures, from screening through end-of-study, that the human subject must undergo in the research project, including study visits, drug treatments, randomization and the procedures that are part of standard of care. Specify which procedures are for research and which are standard of care. Please note: The box below is for text only. If you would like to add tables, charts, etc., attach those files in the Attachment section (#16).

- An evaluation is completed at SSM Cardinal Glennon (CG), Fetal Care Institute (FCI) of a woman who has decided to have open fetal surgery to complete a fetal repair before the infant is born. (SOC)
- She will be approached in the FCI clinic setting by a member of the research team.

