c) If the proposed study is a clinical trial where a drug, vaccine, device or other treatment is compared to a placebo group or comparison treatment group, what are the guidelines or endpoints by which early decisions regarding efficacy or lack of efficacy can be made? For example, it may be reasonable to stop enrollment on a study when efficacy has already been clearly demonstrated, to avoid unnecessary enrollments of additional subjects. Alternatively, it may be reasonable to stop enrollment when it is clear that efficacy will never be demonstrated, given the statistical power of the study as designed. Describe the guidelines that are in place to assist in making these determinations, if relevant to the proposed study.

n/a

d) Describe how data analysis will be performed (statistical tests, methods of evaluating data) and indicate the smallest group/unit for which separate reporting will occur. For studies involving a questionnaire, if data and reliability information are available, please describe or provide references. For full board, unfunded studies describe sample size determination and power analysis. If none, please justify.

Data will be collected from patient interview/questionnaire (by phone). Data collection will be transcribed to an Excel spreadsheet. Data will be now be transcribed to REDCap. Each patient will have separate reporting.
All patients will be used for this descriptive study.
Continuous data (thickness of uterine wall: myometrium) will analyzed for average, mean, maximum and minimum and correlated with any known complications: dehiscence/rupture/repair at cesarean delivery.
Numerical data similarly.
Collected data will be analyzed using standard statistical methods. (averages, mean, max, min).

Please save frequently

e) State if deception (including incomplete disclosure of study purpose/procedures) will be used. If so, describe the nature of the deception and provide a rationale for its use. Also, describe debriefing procedures or justify a waiver of the requirement to debrief. NOTE: for studies using deception, an alteration of consent must be justified in the Informed Consent section of the protocol (#13) and the debriefing script/statement must be uploaded in the Attachments section (#16). See IRB Deception Guidelines.

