*** Subject Population ***

8. Subject Population (continued)

Protocol Title: Evaluation of Hysterotomy Site after Open Fetal Surgery

Page numbers from a sponsor's protocol/grant may be referenced in 8h.

h) Inclusion and Exclusion Criteria.

Identify inclusion criteria.

FCI evaluation

Received Open Fetal Surgery

Open fetal surgery of myelomeningocele: maternal age of ≥ 18 yrs. and ≤ 50 yrs.

If a woman < 18 years old presented with a fetal tumor requiring open fetal repair, this would be done if deemed ethically sound by both CGCMC and SMHC ethics committees. Given this, then the patient may qualify for this study. This is a RARE event.

Agree to travel to Saint Louis for sonohysterogram 6 or more months after delivery.

Identify exclusion criteria.

Presently pregnant

Hysterectomy after delivery

Menopause

Using IUD (Intrauterine Device) for birth control

There is no exclusion criteria for infants

i) Compensation. Explain the amount and schedule of compensation, if any, that will be paid for participation in the study. Include provisions for prorating payment.

You will not be paid to take part in this study. However, travel and lodging expenses will be covered up to 400 dollars.

Travel distances will be calculated using Google maps.

If your primary residence is 50 miles or less you will receive a \$50 dollar VISA card.

If your primary residence is 51 to 100 miles you will receive a \$100 dollar VISA card.

If your primary residence is 101 to 150 miles you will receive a \$150 dollar VISA card.

If your primary residence is 151 to 200 miles you will receive a \$200 dollar VISA card.

If your primary residence is 201 to 250 miles you will receive a \$250 dollar VISA card.

If your primary residence is 251 to 300 miles you will receive a \$300 dollar VISA card.

If your primary residence is 301 to 350 miles you will receive a \$350 dollar VISA card.

If your primary residence is 351 miles or greater you will receive a \$400 dollar VISA card.

The costs of sonohysterogram and the pregnancy test used in this research study are provided at no cost to you or your insurance carrier. The costs are covered by a grant from the SSM Health St. Mary's Foundation and the Saigh Foundation.

Annual phone calls are made to you by a member of the research team to monitor pregnancy status until you become pregnant, have a hysterectomy or approach menopause.

j) Describe who will cover study related costs. Explain any costs that will be charged to the subject.

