 - . This information must be disclosed on the SLU confidential Conflict of Interest Disclosure Form and reviewed by the COIRC before accruing research subjects in this study. If your current Disclosure Form does not contain this information, you are required to submit an updated Disclosure Form to the COIRC.
2. You may not begin your study until your disclosure form has been reviewed and any required management plan has been approved by the COIRC for this study. To initiate COIRC review of your study, please contact [contact].

* * * Informed Consent * * *

13. Informed Consent

Protocol Title: Evaluation of Hysterotomy Site after Open Fetal Surgery

Federal regulations require that informed consent be obtained from individuals prior to their participation in research unless the IRB grants a waiver of consent. Answer the questions, below, then click Add to provide the necessary consent documents and information regarding subject consent. Multiple consents/waivers may be added, but they must be uploaded one at a time.

NOTE: You may refer to the SLU IRB Guidance for Obtaining Informed Consent for considerations regarding the consent/assent process.

State N/A if not applicable.

1) How is consent being obtained? When and where will the discussion take place? If the study involves a non-English Speaking participant/population, please include details about plans for translated materials and interpreters to be used (see SLU Guidelines for Involving Non-English Speaking Subjects for more details).

Retrospectively, consent will be obtained by phone contact from a member of the research team, the study will be described and they will be asked if they are interested in participating. All questions will be answered. The consent, HIPAA authorization, and Notice of Privacy Practices will be mailed to them with highlighted areas needing to be signed. An addressed return envelope will be included for their convenience when returning the signed information to the FCI. When the consent is returned it will be dated, signed, copied and the copy will be mailed to the mother.

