Prospectively, the subject will be consented in clinic after she has decided to have open fetal surgery. If time does not allow for consent prior to surgery, consent will be completed at a follow-up appointment. A member of the research team will consent for the study, give a Notice of Privacy Practices, and the obtain the HIPAA authorization. A signed copy of the consent, HIPAA authorization and Notice of Privacy Practices will be given to the subject. Mothers will be directed to the PI if there are any questions or concerns regarding this research study.

Retrospectively, mothers who have previously consented for this study and informed of the change in protocol by phone will be asked if there were any questions. A verbal consent will be requested and read back for the waiver of consent for this subgroup of the protocol and documented in the research record.

2) If the study involves adults unable to consent for themselves (whether diminished capacity to consent is temporary, permanent, progressive or fluctuating), please address the following: a) how is capacity to provide consent being assessed (initially and throughout study, if applicable); b) if unable to provide consent, how is LAR being determined (See SLU LAR Guidelines); c) if unable to provide consent, will assent be obtained and if not, why not?; d) if unable to provide assent, will dissent be honored and if not, why not? Note: participants initially unable to provide consent for themselves are expected to be given an opportunity to provide consent once capacity is gained. See SLU Guidelines for Adults Unable to Provide Consent for additional detail.

n/a

Note: Any assent documents which will be used per the Adults Unable to Provide Consent guidance, should be appropriately named and uploaded using the Add button and the Consent drop down menu

Protocol Title: Evaluation of Hysterotomy Site after Open Fetal Surgery

selection.

Informed Consent

Title	Consent Type	Attached Date
Waiver 22581	Waiver of Written Consent	
Approved_22581 consent version 8	Consent	05/05/2017

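### Section 3d pools clinic-enrolled and phone-enrolled women and does not separate scans taken after a further pregnancy, although thickness is meant to inform risk in future pregnancies

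*Combined protocol and SAP*

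**What the plan says.** - **Design (2c).** "This is an Investigator initiated, prospective study reviewing medical records and performing a sonohysterogram on non-pregnant women at 6 or more months after delivery". The procedures in 3b describe only an approach in the clinic by women who have decided on surgery.
- **Consent (13, item 1).** There are two ways in. One is the clinic: "Prospectively, the subject will be consented in clinic after she has decided to have open fetal surgery". The other is by telephone and post: "Retrospectively, consent will be obtained by phone contact from a member of the research team". A further paragraph that also opens with the word retrospectively deals with women already in the study who are told of a protocol change. It is not a third route.
- **Analysis (3d).** "All patients will be used for this descriptive study". Myometrial thickness "will analyzed for average, mean, maximum and minimum and correlated with any known complications: dehiscence/rupture/repair at cesarean delivery". No summary by enrolment route is described.
- **Eligibility (8h).** The exclusions are current pregnancy, menopause, an IUD and "Hysterectomy after delivery". A later pregnancy that has already ended is not listed.
- **Scan timing (2b, 3b).** Six months or more after delivery, with no upper limit.
- **Intended use (1a, 10a).** Thickness is to improve prediction for future pregnancies and to support advice about them if it proves to correlate with later uterine compromise.

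**The concern.** A woman who joins by phone may have had another pregnancy since the index delivery. Section 3f says later deliveries are by cesarean, so by the time of her scan the uterus has been stretched and incised again. That is a different measurement from one taken before any further pregnancy, and 3d would put both into the same mean, minimum and maximum. If a complication at that later delivery is among those correlated with thickness, the scan follows the event it is supposed to predict.

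A second problem is who is missing. A woman with a hysterectomy before phone contact cannot enter, and nothing in the plan counts her. Section 1a aims to look at all women who had open fetal surgery at the centre, and 2b names complications of dehiscence or rupture as an outcome. An uncounted loss that may be related to scar failure therefore bears directly on what the study reports.

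**Working it through.** The plan has no sample-size or precision calculation to reproduce. The first two steps compare sections; the last two show ranges under stated assumptions.

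**1. Can a scan follow a further pregnancy?** Yes. The window in 2b and 3b is open-ended, and 8h bars only a pregnancy present at the time. Clinic-route women are telephoned at five months to book the scan (3b), and a woman found pregnant at the scan is removed (9, items 9 and 10), so a completed intervening pregnancy is less likely on that route. It is not ruled out. For phone-route women no contact window is stated.

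**2. What does 3d do with such a scan?** Three time orders are possible:
- a complication at the index delivery, which precedes every scan;
- a complication at a later delivery that precedes the scan;
- a complication at a later delivery that follows the scan.

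Section 3d refers to any known complication at cesarean delivery and does not distinguish these. Only the third can support a statement that thickness predicts later dehiscence or rupture.

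**3. Effect on mean thickness.** Let g be the share of scans taken after an intervening pregnancy and d the difference in thickness. The pooled mean moves by g × d. The documents give neither. Assuming d = 1 SD, the shift is 0 at g = 0 and 0.25 × 1 = 0.25 SD at g = 0.25.

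**4. Effect of selective entry on a complication rate.** Inputs:
- p = 0.28, the only rate given (3f: unpublished, another centre, dehiscence and/or rupture at delivery);
- f, the share enrolled by phone (assumed);
- r, the chance that a woman with a complication enters by phone, relative to one without (assumed).

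Phone-group rate = p·r / (p·r + 1 − p). Pooled rate = f × phone-group rate + (1 − f) × p.

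Example with f = 0.25 and r = 0.5: 0.14 / (0.14 + 0.72) = 0.163; pooled 0.25 × 0.163 + 0.75 × 0.28 = 0.251.

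Example with f = 0.50 and r = 2: 0.56 / (0.56 + 0.72) = 0.4375; pooled 0.50 × 0.4375 + 0.50 × 0.28 = 0.359.

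| r | Phone-group rate | Pooled, f = 0.25 | Pooled, f = 0.50 |
|---|---|---|---|
| 2 | 43.8% | 31.9% | 35.9% |
| 1 | 28.0% | 28.0% | 28.0% |
| 0.75 | 22.6% | 26.6% | 25.3% |
| 0.5 | 16.3% | 25.1% | 22.1% |
| 0 | 0% | 21.0% | 14.0% |

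If women with complications differ in thickness by 1 SD (assumed), selective entry moves the pooled mean by 1 × (0.28 − 0.251) = 0.03 SD at f = 0.25, r = 0.5, and by 0.14 SD at f = 0.50, r = 0. For scale, if all 35 accrued subjects are mothers, the exact 95% interval for 10/35 is 14.6% to 46.3%.

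**The case against.** **The primary measurement is not known at enrolment.** A reader might infer that phone-route women are enrolled with their outcomes already known. The documents do not support that for scar depth and location: the sonohysterogram is a research procedure outside standard care (3f) and follows consent on either route. Only delivery data, and perhaps a later pregnancy, can pre-date the call. This stands. It does not remove the problem of an intervening pregnancy, which affects the scan itself.

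**The exclusions apply to both routes.** A clinic-consented woman who has a hysterectomy before the scan supplies no thickness either. This stands too, so splitting by route does not cure selection on having a scannable uterus. The difference is that she is a known participant whose loss can be counted, whereas a woman ineligible before the call need leave no trace.

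**Complications at the index cesarean are not an exclusion.** Severe cases are barred only where they led to hysterectomy. Selective entry is possible but not shown, and r = 1 gives no bias.

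**The study is descriptive and small.** At f = 0.25 and r = 0.5 the shift is 2.9 points, well inside the sampling uncertainty. That limits the urgency, but 3d still plans a correlation and 1a and 10a still give it a predictive purpose.

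**The attachments are not available.** The datasheet and interview questions may already capture route and interval pregnancies, and 3d says each patient will be reported separately. The field may exist; the rule for using it does not appear in 3d.

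**Conclusion.** The point holds as a gap in the analysis rule. Followed as written, 3d lets thickness measured after a further pregnancy and cesarean be averaged with thickness measured before any, and be correlated with complications that came first. That follows from the text and does not depend on how many women were phoned, although its practical effect does: if no scanned woman had an intervening pregnancy, the effect is nil.

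Selection through uncounted women can also bias the pooled results. Its size and direction cannot be determined. The range of 14.0% to 35.9% around 28% rests entirely on assumed f and r and on another centre's unpublished rate.

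Two stronger readings should be resisted. Bias is not certain, because the documents give no number phoned, no contact window and no evidence of differential entry. Nor can one say that rates of hysterectomy or later pregnancy are understated by a given fraction through pre-contact time. The plan estimates no rate over time, hysterectomy is an end of follow-up and not a listed outcome, and completed pregnancies can enter by phone, so that period is not free of pregnancies by design. Starting time at risk at consent matters only if an event rate over time is actually reported.

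**What to change.** In 3d:
1. Record enrolment route and any pregnancy between the index delivery and the scan, if the datasheet does not already do so.
2. Base the main thickness summary on women with no intervening pregnancy, and list the others separately.
3. For any statement that thickness predicts later dehiscence or rupture, use only pregnancies that begin after the scan.
4. Tabulate thickness and complications by route as well as overall, with a count of all eligible surgeries and the reasons for non-inclusion.

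In 2c, describe both routes, so that the design statement agrees with section 13.

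The cost is at most two data fields, a screening count and some analysis wording, and slightly fewer women in the main summary. No visit or procedure changes, and it can be done with accrual closed.

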***** Assent *******14. Assent**

Complete this section if your study includes minors. The Assent Form Template provides guidelines for writing assent documents.

1. Will minors be asked to give assent, then consent once they reach adulthood? If not, please justify. If not capable to provide assent initially, please address whether assent will be obtained as the minor gains capacity. Note: children who reach the age of adulthood during participation should be given the opportunity to provide consent as parent/guardian consent no longer applies. If obtaining consent would be impracticable (e.g., this is a registry with data/specimen obtained long ago), a waiver of consent should be added for IRB review. See SLU Guidelines for Research Involving Minors for additional detail.

Mothers' infants are to young to require assent.

2. If minors are asked to assent and do not wish to participate, will they still be accrued in the study? If yes, justify.

n/a

3. How will the minor's ability to give assent be assessed? (Consider the age and maturity of the minors as well as their physical or mental condition). If capacity is fluctuating, please explain how capacity will be assessed throughout the study.

n/a

Note: For studies that require a discussion about reproductive risks, note that the conversation with the minor should take place separately from the parents. Also, if a minor will reach adulthood (18 in Missouri) during the course of the study, they will need to be asked to consent as an adult at that time to continue in the study.

***** HIPAA *****

Protocol Title: Evaluation of Hysterotomy Site after Open Fetal Surgery

15. HIPAA

Studies that access, receive or collect protected health information (PHI) are subject to HIPAA regulations. PHI is health information with one or more personal identifiers. For more information visit the IRB HIPAA page or refer to the SLU IRB HIPAA Guidance.

1. Will health information be accessed, received or collected?

No health information. HIPAA does not apply.

Yes (continue to question 2).

2. Which personal identifiers will be received or collected/recorded?

No identifiers. I certify that no identifiers from the list below will be received or collected and linked to health information. (Skip remainder of page).

Limited identifiers will be received or collected/recorded (study will likely require a data use agreement). Select Data Use Agreement- INTERNAL or Data Use Agreement- EXTERNAL as appropriate, below.

City/State/Zip codes

Person-specific dates (e.g., date of birth, dates of service, admission/discharge dates, etc.)

Age (if subjects are 90+ years)

At least one direct identifier will be received or collected/recorded.

Names

Social Security numbers

Telephone numbers

Linkable code or any other unique identifying number (note this does not mean the unique code assigned by the Investigator(s) to code the research data)

All geographic subdivisions smaller than a State, including street address, city, county, precinct, zip code, and their equivalent geocodes, except for the initial three digits of a zip code, if, according to the current publicly available data from the Bureau of the Census: (1) The geographic unit formed by combining all zip codes with the same three initial digits contains more than 20,000 people; and (2) The initial three digits of a zip code for all such geographic units containing 20,000 or fewer people is changed to 000

All elements of dates (except year) for dates directly related to an individual, including birth date, admission date, discharge date, date of death; and all ages over 89 and all elements of dates (including year) indicative of such age, except that such ages and elements may be aggregated into a single category of age 90 or older

Fax numbers

Electronic mail addresses

Medical record numbers

Health plan beneficiary numbers

Account numbers

Certificate/license numbers

Vehicle identifiers and serial numbers, including license plate numbers

Device identifiers and serial numbers

Web Universal Resource Locations (URLs)

Internet Protocol (IP) address numbers

Protocol Title: Evaluation of Hysterotomy Site after Open Fetal Surgery

Biometric identifiers, including finger and voice prints
Full face photographic images and any comparable images

If you are receiving or collecting/recording health information and at least one personal identifier, please continue to complete the sections, below.

3. Sources of Protected Health Information:

- Hospital/medical records for in or out patients
- Physician/clinic records
 - Laboratory, pathology and/or radiology results
 - Biological samples
- Interviews or questionnaires/health histories
 - Mental health records
 - Data previously collected for research purposes
 - Billing records
- Other

Please describe:

Sonohysterogram

4. If data will be shared outside the research team and the study involves PHI indicate how the research team will share the information.

- Not applicable (continue to question 5).

Only linkable code that can link data to the identity of the subject. A code access agreement or business associate agreement may be needed when data are shared with other non-SLU entities. If necessary, the agreement can be added and uploaded in item #5, below.

Limited identifiers: Zip codes, dates of birth, or other dates only. The study qualifies as a Limited Data Set. A data use agreement may be needed when data are shared with other non-SLU entities. If necessary, the agreement can be added and uploaded in item #5, below, using DUA-external option.

With unlimited identifiers. The consent document and HIPAA Authorization form must describe how the information will be disclosed.

5. HIPAA Documentation is required for this study. Use the table below to add HIPAA Documents for your study.

HIPAA Documents

HIPAA Documents	Title	Attached Date
HIPAA Authorization	Approved_22581_HIPAA_Version_2	03/25/2013

Protocol Title: Evaluation of Hysterotomy Site after Open Fetal Surgery

* * * Event History * * *

Event History

Date	Status	View Attachments	Letters
12/20/2017	CLOSED		
12/20/2017	FINAL FORM APPROVED	Y	Y
12/20/2017	FINAL FORM REVIEWER(S) ASSIGNED		
12/19/2017	FINAL FORM SUBMITTED	Y	
12/19/2017	FINAL FORM CREATED		
06/30/2017	AMENDMENT 8 FORM APPROVED	Y	Y
06/30/2017	AMENDMENT 8 FORM REVIEWER(S) ASSIGNED		
06/26/2017	AMENDMENT 8 FORM SUBMITTED (CYCLE 1)	Y	
06/23/2017	AMENDMENT 8 FORM PANEL MANAGER REVIEW		
06/15/2017	AMENDMENT 8 FORM SUBMITTED	Y	
05/24/2017	AMENDMENT 8 FORM CREATED		
05/05/2017	AMENDMENT 7 FORM APPROVED	Y	Y
05/04/2017	AMENDMENT 7 FORM REVIEWER(S) ASSIGNED		
04/26/2017	AMENDMENT 7 FORM SUBMITTED (CYCLE 1)	Y	
04/21/2017	AMENDMENT 7 FORM PANEL MANAGER REVIEW		
04/17/2017	AMENDMENT 7 FORM PANEL REASSIGNED		
04/17/2017	AMENDMENT 7 FORM SUBMITTED	Y	
04/13/2017	AMENDMENT 7 FORM CREATED		
01/20/2017	CONTINUING REVIEW 4 FORM APPROVED	Y	Y
01/06/2017	CONTINUING REVIEW 4 FORM REVIEWER(S) ASSIGNED		

Protocol Title: Evaluation of Hysterotomy Site after Open Fetal Surgery

01/06/2017	CONTINUING REVIEW 4 FORM PANEL MANAGER REVIEW		
01/03/2017	CONTINUING REVIEW 4 FORM PANEL REASSIGNED		
12/28/2016	CONTINUING REVIEW 4 FORM SUBMITTED	Y	
12/06/2016	CONTINUING REVIEW 4 FORM CREATED		
08/25/2016	AMENDMENT 6 FORM APPROVED	Y	Y
08/25/2016	AMENDMENT 6 FORM REVIEWER(S) ASSIGNED		
08/25/2016	AMENDMENT 6 FORM SUBMITTED (CYCLE 1)	Y	
08/25/2016	AMENDMENT 6 FORM PANEL MANAGER REVIEW		
08/25/2016	AMENDMENT 6 FORM PANEL MANAGER REVIEW		
08/22/2016	AMENDMENT 6 FORM SUBMITTED	Y	
08/11/2016	AMENDMENT 6 FORM CREATED		
03/03/2016	AMENDMENT 5 FORM APPROVED	Y	Y
03/02/2016	AMENDMENT 5 FORM REVIEWER(S) ASSIGNED		
02/29/2016	AMENDMENT 5 FORM PANEL REASSIGNED		
02/29/2016	AMENDMENT 5 FORM SUBMITTED	Y	
02/29/2016	AMENDMENT 5 FORM CREATED		
02/10/2016	CONTINUING REVIEW 3 FORM APPROVED	Y	Y
02/10/2016	CONTINUING REVIEW 3 FORM REVIEWER(S) ASSIGNED		
02/05/2016	PROTOCOL EXPIRED	Y	
02/02/2016	CONTINUING REVIEW 3 FORM CONTINGENT		
01/22/2016	CONTINUING REVIEW 3 FORM REVIEWER(S) ASSIGNED		
01/22/2016	CONTINUING REVIEW 3 FORM PANEL MANAGER REVIEW		
01/08/2016	CONTINUING REVIEW 3 FORM PANEL REASSIGNED		

Protocol Title: Evaluation of Hysterotomy Site after Open Fetal Surgery

01/07/2016	CONTINUING REVIEW 3 FORM SUBMITTED	Y	
12/07/2015	CONTINUING REVIEW 3 FORM CREATED		
06/04/2015	AMENDMENT 4 FORM APPROVED	Y	Y
06/03/2015	AMENDMENT 4 FORM REVIEWER(S) ASSIGNED		
06/02/2015	AMENDMENT 4 FORM PANEL REASSIGNED		
06/01/2015	AMENDMENT 4 FORM SUBMITTED	Y	
05/29/2015	AMENDMENT 4 FORM CREATED		
01/08/2015	CONTINUING REVIEW 2 FORM APPROVED	Y	Y
12/19/2014	CONTINUING REVIEW 2 FORM REVIEWER(S) ASSIGNED		
12/17/2014	CONTINUING REVIEW 2 FORM PANEL MANAGER REVIEW		
12/15/2014	CONTINUING REVIEW 2 FORM PANEL REASSIGNED		
12/15/2014	CONTINUING REVIEW 2 FORM PANEL REASSIGNED		
12/15/2014	CONTINUING REVIEW 2 FORM SUBMITTED	Y	
12/09/2014	CONTINUING REVIEW 2 FORM CREATED		
07/28/2014	AMENDMENT 3 FORM APPROVED	Y	Y
07/25/2014	AMENDMENT 3 FORM REVIEWER(S) ASSIGNED		
07/24/2014	AMENDMENT 3 FORM PANEL REASSIGNED		
07/21/2014	AMENDMENT 3 FORM SUBMITTED	Y	
07/21/2014	AMENDMENT 3 FORM CREATED		
02/05/2014	CONTINUING REVIEW 1 FORM APPROVED	Y	Y
02/05/2014	PROTOCOL EXPIRED		
01/24/2014	CONTINUING REVIEW 1 FORM REVIEWER(S) ASSIGNED		
01/22/2014	CONTINUING REVIEW 1 FORM PANEL MANAGER REVIEW		

Protocol Title: Evaluation of Hysterotomy Site after Open Fetal Surgery

01/22/2014	CONTINUING REVIEW 1 FORM PANEL REASSIGNED		
01/09/2014	CONTINUING REVIEW 1 FORM RESUBMITTED	Y	
12/20/2013	CONTINUING REVIEW 1 FORM RETURNED		
12/16/2013	CONTINUING REVIEW 1 FORM SUBMITTED	Y	
12/09/2013	CONTINUING REVIEW 1 FORM CREATED		
10/11/2013	AMENDMENT 2 FORM APPROVED	Y	Y
10/09/2013	AMENDMENT 2 FORM REVIEWER(S) ASSIGNED		
10/08/2013	AMENDMENT 2 FORM SUBMITTED (CYCLE 2)	Y	
09/24/2013	AMENDMENT 2 FORM SUBMITTED (CYCLE 1)	Y	
09/19/2013	AMENDMENT 2 FORM CONTINGENT		
09/06/2013	AMENDMENT 2 FORM REVIEWER(S) ASSIGNED		
09/06/2013	AMENDMENT 2 FORM PANEL REASSIGNED		
09/06/2013	AMENDMENT 2 FORM REVIEWER(S) ASSIGNED		
09/03/2013	AMENDMENT 2 FORM RESUBMITTED	Y	
08/29/2013	AMENDMENT 2 FORM RETURNED		
08/27/2013	AMENDMENT 2 FORM SUBMITTED	Y	
08/15/2013	AMENDMENT 2 FORM CREATED		
07/15/2013	REPORT 1 FORM DELETED		
07/05/2013	AMENDMENT 1 FORM APPROVED	Y	Y
07/05/2013	AMENDMENT 1 FORM REVIEWER(S) ASSIGNED		
07/01/2013	AMENDMENT 1 FORM PANEL REASSIGNED		
07/01/2013	AMENDMENT 1 FORM PANEL REASSIGNED		
07/01/2013	AMENDMENT 1 FORM SUBMITTED	Y	
06/20/2013	REPORT 1 FORM CREATED		
06/07/2013	AMENDMENT 1 FORM CREATED		

Protocol Title: Evaluation of Hysterotomy Site after Open Fetal Surgery

03/26/2013	NEW FORM APPROVED	Y	Y
03/25/2013	NEW FORM REVIEWER(S) ASSIGNED		
02/07/2013	NEW FORM CONTINGENT		
01/25/2013	NEW FORM REVIEWER(S) ASSIGNED		
01/09/2013	NEW FORM PANEL MANAGER REVIEW		
01/07/2013	NEW FORM PANEL REASSIGNED		
01/07/2013	NEW FORM PANEL ASSIGNED		
01/04/2013	NEW FORM SUBMITTED	Y	
01/04/2013	NEW FORM PREREVIEWED		
01/03/2013	NEW FORM PREAPPROVAL		
09/10/2012	NEW FORM CREATED		

SLU eIRB
